2.2. Study Objective(s) and Endpoint(s)

Objectives	Endpoints
Primary Objectives	Primary Endpoints

 To demonstrate non-inferiority of GSK1278863 to epoetin beta pegol based on hemoglobin (Hgb) in ND subjects 	
 Mean Hgb during the primary efficacy evaluation period (Weeks 40 to 52)
Principal Secondary Objectives	Principal Secondary Endpoints

 To demonstrate superiority of GSK1278863 to epoetin beta pegol in terms of achievement/maintenance of target Hgb in ND subjects 	
 Number (%) of subjects with mean Hgb in the target range (11.0-13.0 g/dL) during the primary efficacy evaluation period (Weeks 40 to 52)
Other Secondary Objectives	Other Secondary Endpoints

 To evaluate the appropriateness of the starting dose of GSK1278863 in ND subjects using epoetin beta pegol as control To evaluate the appropriateness of the starting dose of GSK1278863 in PD subjects 	
 Change in Hgb from baseline to Week 4 (Hgb increase rate) Number (%) of subjects by Hgb change category in Hgb from baseline to Week 4

 To evaluate dose adjustments of GSK1278863 in ND subjects using epoetin beta pegol as control To evaluate dose adjustments of GSK1278863 in PD subjects 	
 Distribution of the dose level Duration of treatment interruption due to Hgb >13 g/dL Frequency of dose adjustments

 To evaluate the overall Hgb control by GSK1278863 in ND subjects using epoetin beta pegol as control To evaluate the overall Hgb control by GSK1278863 in PD subjects 	
 Hgb at each assessment time point and change in Hgb from baseline to each assessment time point Number (%) of subjects with Hgb within the target range (11.0-13.0 g/dL) at each assessment time point Proportion (%) of time with Hgb within the target range (11.0-13.0 g/dL) in the primary efficacy evaluation period (Weeks 40 to 52) Time (number of days) to the lower Hgb target (11.0 g/dL) Number (%) of subjects who have an Hgb level of less than 7.5 g/dL Number (%) of subjects who have an Hgb increase of more than 2 g/dL over any 4 weeks before Week 52 Number (%) of subjects who achieve an Hgb level of more than 13.0 g/dL and number of episodes

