Number of dose adjustment to reach the lower Hgb target (11.0 g/dL) by prior ESA use			Y			
Number (%) of subjects with each dose at each assessment visit			Y	Y		
Number(%) of subjects with each dose at each assessment visit by prior ESA ^[1]			Y	Y		
Hgb and Dose						
Profiles of Hgb and dose over time					Y	
Iron Use						
Dose of oral iron (mg) during the treatment period and the primary efficacy evaluation period (Week 40 to 52)			Y			
Change from baseline in dose of oral iron (mg) during the treatment period and the primary efficacy evaluation period			Y			
Dose of oral iron (mg) during the treatment period and the primary efficacy evaluation period (Week 40 to 52) by Baseline Iron Use			Y			
Number (%) of subjects who use iron during the treatment period and the primary efficacy evaluation period (Week 40 to 52)			Y			
Number (%) of subjects who use iron during the treatment period and the primary efficacy evaluation period (Week 40 to 52) by Baseline Iron Use			Y			

[Endpoint / Parameter/ Display Type]	Absolute					
	Stats Analysis		Summary		Individual	
	T	F	T	F	F	L
Iron Parameters (ferritin, TSAT, hepcidin, serum iron, TIBC)						
Raw observed value at each assessment visit			Y	Y		Y
Raw observed value at each assessment visit by Subgroup ^[7]			Y	Y		
Change from baseline at each assessment visit	Y	Y	Y			
Change from baseline at each assessment visit by Subgroup ^[7]	Y	Y ^[8]	Y			

NOTES :

- T = Table, F = Figure, L = Listing, Y = Yes display generated.
- Stats Analysis = Represents TFL related to any formal statistical analyses (i.e. modelling) conducted.
- Summary = Represents TFL related to any summaries (i.e. descriptive statistics) of the observed raw data.
- Individual = Represents FL related to any displays of individual subject observed raw data.

[1] prior ESA use, prior ESA dose, prior ESA type, and ERI

[2] <=-1, >-1 to -0.5, >-0.5 to 0, >0 to 0.5, >0.5 to 1, >1 g/dL, within ± 0.5 g/dL and over ± 1 g/dL for Week 2

<=-2, >-2 to -1, >-1 to 0, >0 to 1, >1 to 2, >2 g/dL, within ± 1 g/dL and over ± 2 g/dL for Week 4

[3] Not only within the target range, but also with above and below target range will be assessed.

[4] Rosendaal method will be used (See Section 15.6.3).

[5] Kaplan-Meier method will be used to estimate P25, median and P75. Subjects within target range at baseline and subjects who could not reach lower target will be regarded as censored.

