7.3.2. Summary Measure

Hgb at each assessment visit

The values will be summarized using mean, standard deviation, 95%CI, minimum, P25, median, P75, and maximum at each assessment visit by treatment group. The summary will also be provided by prior ESA use, prior ESA dose, prior ESA type, and ERI. Graphical summaries will be provided using mean and 95% CI over time. The graphical summaries will also be provided by prior ESA use. The value at Wk2 (only for Cohort 3) will be provided only in summary (not in graphical summary).

Change from baseline at each assessment visit

The values will be summarized using mean, standard deviation, 95%CI, minimum, P25, median, P75, and maximum at each assessment visit by treatment group. The summary will also be provided by prior ESA use, prior ESA dose, prior ESA type, and ERI. Graphical summaries will be provided using mean and 95% CI over time. The graphical summaries will also be provided by prior ESA use. The value at Wk2 (only for Cohort 3) will be provided only in summary (not in graphical summary).

Number (%) of subjects by Hgb change from baseline category at Week 2 and 4

The number and percentage of subjects within each category will be provided by treatment group and the categories will be classified into 6 (i.e., ≤ -1 , > -1 to -0.5 , > -0.5 to 0 , > 0 to 0.5 , > 0.5 to 1 , > 1 g/dL for Week 2, ≤ -2 , > -2 to -1 , > -1 to 0 , > 0 to 1 , > 1 to 2 , > 2 g/dL for Week 4). In addition, 'within ± 1 g/dL (i.e., ≤ -1 and ≥ 1)' and 'over ± 2 g/dL (i.e., < -2 and > 2)' categories for Week 4 and 'within ± 0.5 g/dL (i.e., ≤ -0.5 and ≥ 0.5)' and 'over ± 1 g/dL (i.e., < -1 and > 1)' categories for Week 2 will be provided. The summary will also be provided by prior ESA use, prior ESA dose, prior ESA type, and ERI.

Number (%) of subjects with Hgb within the target range at each assessment visit

The number and percentage of subjects with Hgb within, above and below the target range will be summarized at each assessment visit by treatment group. Graphical summaries over time will also be produced.

Time (%) in Hgb target range during the primary efficacy evaluation period

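### SAP Section 7.3.2 reverses the inequalities that define the two supplementary within-band rows for Hgb change (±1 g/dL at Week 4, ±0.5 g/dL at Week 2)

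*SAP*

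**What the plan says.** Section 2.2 lists, under the starting-dose objectives for ND and PD subjects, the secondary endpoint "Number (%) of subjects by Hgb change category in Hgb from baseline to Week 4". Section 7.3.2 delivers it through six ordered categories per visit, from ≤ -2 to > 2 g/dL at Week 4 and from ≤ -1 to > 1 g/dL at Week 2.

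The same paragraph then adds two summary rows per visit and gives each an explicit rule:

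- Week 4, inside the band: "within ± 1 g/dL (i.e., ≤ -1 and ≥ 1"
- Week 4, large change: "over ± 2 g/dL (i.e., < -2 and > 2"
- Week 2, inside the band: "within ± 0.5 g/dL (i.e., ≤ -0.5 and ≥ 0.5"
- Week 2, large change: "over ± 1 g/dL (i.e., < -1 and > 1"

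Note [2] to the table in Section 7.3.1 repeats the labels without inequalities: "within ± 1 g/dL and over ± 2 g/dL for Week 4" and "within ± 0.5 g/dL and over ± 1 g/dL for Week 2". Section 15.6.3, which holds the Hgb derivations, has no entry for these rows. The rows belong to Tables 2.32 to 2.35 in Section 15.10.4.2. All four tables cover Week 4. Only 2.32 and 2.34 (ITT) also cover Week 2.

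**The concern.** In both within-band rows the label and its own explanation contradict each other. The label names changes close to zero. The inequalities point away from zero on both sides, and no change can be at or below the negative limit and at or above the positive limit at once.

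A programmer who follows the written rule gets either an empty row or a row that counts the subjects the label leaves out. Because Section 7.3.2 is the only place where the rule is given as inequalities, correct output depends on someone noticing the conflict and departing from the plan. The row in question shows how many subjects stayed near their baseline Hgb after the starting dose, by treatment and, in Tables 2.34 and 2.35, by prior ESA.

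**Working it through.** The SAP gives no figure to reproduce here. The check is set logic on the written rules, followed by an illustration of size.

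**Inputs from Section 7.3.2.** Within-band limits w = 1 (Week 4) and 0.5 (Week 2). Large-change limits o = 2 (Week 4) and 1 (Week 2). The rules are evaluated on changes from -3.0 to +3.0 g/dL in steps of 0.1, which is 61 values. The worked examples in Section 15.6.3 also show Hgb to one decimal.

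**Reading 1, intersection:** change ≤ -w and change ≥ w.

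- Week 4: 0 of 61 values.
- Week 2: 0 of 61 values.

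**Reading 2, union:** change ≤ -w or change ≥ w. This is the only reading under which the large-change rules in the same sentence make sense.

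- Week 4: 21 values from -3.0 to -1.0 plus 21 from 1.0 to 3.0 = 42 of 61. Zero is not among them.
- Week 2: 26 + 26 = 52 of 61. Zero is again excluded.
- The large-change row (20 values at Week 4, 40 at Week 2) lies wholly inside the so-called within row, so a subject with a change of +2.5 g/dL at Week 4 would count in both.

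**Band named by the label:** -w ≤ change ≤ w.

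- Week 4: 21 of 61 values. Week 2: 11 of 61. Neither overlaps its large-change row.
- The union result is the complement of this band except at the two end points, which fall in both: 42 + 21 = 63 = 61 + 2, and 52 + 11 = 63 = 61 + 2.

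**Size, under assumed normal changes** (mean m and SD s are my assumptions, not SAP figures). True share = Φ((w - m)/s) - Φ((-w - m)/s). For a continuous variable, union share = 1 - true share.

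| Visit | m, s (g/dL) | True share | Union | Intersection |
|---|---|---|---|---|
| Week 4 | 0, 0.7 | 84.7% | 15.3% | 0% |
| Week 4 | 0.5, 0.7 | 74.6% | 25.4% | 0% |
| Week 4 | 1.0, 1.0 | 47.7% | 52.3% | 0% |
| Week 2 | 0, 0.5 | 68.3% | 31.7% | 0% |
| Week 2 | 0.25, 0.5 | 62.5% | 37.5% | 0% |
| Week 2 | 0.5, 0.7 | 42.3% | 57.7% | 0% |

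Example, Week 4 with m = 1.0 and s = 1.0: Φ(0) - Φ(-2) = 0.500 - 0.023 = 0.477.

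**Relation to the base categories.** The two middle Week 4 categories together cover > -1 to 1, which is 20 grid values. The inclusive band has 21. The only difference is a change of exactly -1.0. At Week 2 the only difference is exactly -0.5 (10 values against 11).

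**The case against.** The strongest reply is that the intent is plain and the slip would show. The labels appear in two sections. An empty within row, or one that swallows the large-change row, would stand out beside six correct categories in the same table. Those categories also let a reader recover the intended share, except for changes exactly at the negative limit. The table shells are separate documents (Section 15.11) and may already be right. All of this stands, and it limits the consequence. It does not remove the contradiction, because the only explicit rule in the SAP is the wrong one.

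A misread sign in the text taken from the PDF cannot be ruled out. It is unlikely: the same reversal occurs twice, while the neighbouring inequalities run the right way. A glance at the PDF settles it.

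A reader might infer three stronger points, which the SAP does not support:

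- **That the starting-dose endpoint itself is broken.** The six categories that deliver the Section 2.2 endpoint are usable as written, and the within rows are introduced as additions. Week 2 is not part of that endpoint.
- **That the share of subjects with an acceptable change is misreported.** The SAP nowhere sets ±1 g/dL as a criterion of acceptability.
- **That the six categories must be recut so that the summary rows equal their sums.** Intervals closed on one side are ordinary practice, and the SAP does not promise that the rows add up. That -2.0 falls in the lowest category but not in the large-change row contradicts nothing. A symmetric recut could also move a change of exactly 0 into an increase category.

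**Conclusion.** The point holds as a drafting error with a definite consequence. In Section 7.3.2 the signs of both within-band definitions are reversed, so each row, coded as written, is empty or counts subjects at or beyond the limits. This follows from the text alone and needs no assumption about the data.

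The size does need assumptions. Across Week 4 means of 0 to 1.0 and SDs of 0.7 to 1.0 g/dL, a true share of 48% to 85% would appear as 0% or as 15% to 52%. Across Week 2 means of 0 to 0.5 and SDs of 0.5 to 0.7 g/dL, a true share of 42% to 68% would appear as 0% or as 32% to 58%.

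The reach is narrow: one supplementary descriptive row per visit in Tables 2.32 to 2.35, with no model or test attached. The primary and principal secondary analyses, the six base categories, the large-change rows and the mean change summary are unaffected.

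**What to change.** In Section 7.3.2:

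- Week 4: define within ±1 g/dL as change ≥ -1.0 and ≤ 1.0.
- Week 2: define within ±0.5 g/dL as change ≥ -0.5 and ≤ 0.5.
- In the two large-change definitions, write 'or' between the limits: < -2 or > 2 at Week 4, and < -1 or > 1 at Week 2.

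Leave the six base categories as they are. A table footnote may say that the within row includes its lower limit, so it can differ from the sum of the two middle categories at a change of exactly -1.0 (Week 4) or -0.5 (Week 2). Check that the shell for Tables 2.32 to 2.35 (EFF_T6) follows the corrected rule.

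The cost is one sentence in the SAP, an optional footnote and a check of the shell. No data, sample size or other analysis changes.

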
Overview of Study Design and Key Features	
	
 For ESA users, prior ESA will be replaced with epoetin beta pegol at the equivalent dose once every 4 weeks (Day 1). At Week 2, HemoCue Hgb value will be measured for subjects' safety confirmation. If the measurement shows an Hgb increase of >1.0 g/dL over 2 weeks, the dose of GSK1278863 will be reduced by one step (or treatment interrupted) at Week 4 (Cohort 3 only). 
Maintenance Dose
 
 Epoetin beta pegol will be administered once every 4 weeks from dosing interval change (once every 4 weeks) with Hgb \geq11.0 g/dL to Week 52 in ESA non-users and from Weeks 4 to 52 in ESA users Further details of dosing are provided in the protocol Section 6.4.
Time & Events	
 Refer to Appendix 2: Schedule of Activities
Treatment Assignment	
 The randomization schedule will be generated by GlaxoSmithKline (GSK) using the randomization system (Randall NG). In Cohort 1 and Cohort 3 (ND subjects), subjects will be stratified by the current ESA therapy (ESA non-user or ESA user) and the Hgb level on Day 1 and randomized in a 1:1 ratio to one of the two treatment groups according to the randomization schedule. In Cohort 2 (PD subjects), all eligible subjects will start treatment with GSK1278863 on Day 1.
Interim Analysis	
 No interim analysis is planned.

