5.4. Examination of Covariates, Other Strata and Subgroups

5.4.1. Covariates and Other Strata

The list of covariates and other strata will be used in statistical analyses, the strata will also be used for subgroup analyses.

Randomization is stratified by prior ESA use and baseline Hgb in Cohort 1 and Cohort 3 (ND subjects). Baseline Hgb will be included as a covariate in the primary efficacy analyses. Prior ESA use and baseline Hgb will be included as covariates in the principal secondary efficacy analyses. The reasons why prior ESA use will not be included in the primary analyses are 1) the data for the primary endpoint is longitudinal data and the visit effect and the interaction with visit are important. 2) if including prior ESA use in the analyses the model will be complicate and it will be difficult to interpret the results. While, the data for the principal secondary endpoint is not longitudinal data and it has no visit data. Thus, it will not be complicate even if including prior ESA use in the model.

Category	Details
Strata	ESA use, Baseline Hgb
Covariates	
For primary efficacy analyses:
 
 Mixed model for repeated measurements (MMRM) including covariates of treatment group, baseline Hgb, visit, treatment-by-visit interaction, and baseline Hgb-by-visit interaction will be used. 
For principal secondary efficacy analyses:
 
 Logistic regression model including treatment group, baseline Hgb, and current ESA therapy (presence or absence) as covariates will be used.

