The time (weeks and percent) within/above/below the target range will be summarized by treatment group using mean, standard deviation, minimum, P25, median, P75, and maximum. For the ITT population, the treatment differences (daprodustat – epoetin beta pegol) and the associated 95% CIs for the time (weeks and percentage) within the target range will also be provided. See Section 15.6.3 for details. The summary will also be provided by prior ESA use.

Time (in days) to reach the lower Hgb target (11.0 g/dL)

The time (days) to reach the lower Hgb target will be summarized by treatment group using P25, median, and P75 by Kaplan-Meier method. Kaplan-Meier plot of time to event will be provided using on-therapy Hgb values including unscheduled visits. Subjects who could not reach lower target will be regarded as censored. Subjects who have baseline central laboratory Hgb ≥ 11.0 g/dL will be excluded in this analysis. The summary will also be provided by prior ESA use.

Number (%) of subjects who have an Hgb level of less than 7.5 g/dL

The number and percentage of subjects who have an Hgb level of less than 7.5 g/dL during the treatment period will be summarized by treatment group. On-therapy Hgb values observed in both scheduled and unscheduled visits will be included in the summary.

Number (%) of subjects who have an Hgb increase of more than 2.0 g/dL over any 4 weeks

The number and percentage of subjects who have an Hgb increase of more than 2.0 g/dL over any 4 weeks (excluding Week 2) during the treatment period will be summarized by treatment group. For the ITT population, the odds ratio (daprodustat/epoetin beta pegol) will also be provided with its 95% CI. On-therapy Hgb values will be used for the summary. See Section 15.6.3 for details.

Number (%) of subjects who have an Hgb level of more than 13.0 g/dL and number of episodes

The number and percentage of subjects who have an Hgb level of more than 13.0 g/dL during the treatment period and number of episodes will be summarized by treatment group. On-therapy Hgb values observed in both scheduled and unscheduled visits will be included in the summary.

Scatter plot of Hgb assessments: Central Laboratory vs. HemoCue

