7.3.5. Statistical Analyses / Methods

Details of the planned displays are provided in [Appendix 10](#): List of Data Displays and will be based on GSK data standards and statistical principles.

Unless otherwise specified, endpoints / variables defined in Section 7.3.1 will be summarized using descriptive statistics, graphically presented (where appropriate) and listed.

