Hgb (g/dL)	Lab Date	Study Day	Visit	Hgb increase
9.1	PPD	1	Day 1	Not calculated
9.8		30	Week 4	0.7
11.9		61	Week 8	2.1
12.6		127	Week 16	Not calculated
12.7		158	Week 20	0.1
12.3		183	Week 24	-0.4

- Odds ratio and its 95% CI will be obtained using the same statistical model described in Section 7.2.5.
- When the odds ratio is undefined, it will not be presented.

Scatter plot of Hgb assessments: Central Laboratory vs. HemoCue

- All available pairs of Hgb (i.e. non-missing values in both from central laboratory and from the corresponding HemoCue measurement) will be used, regardless of treatment groups and visits. The figure will include a linear regression line with 95% CI band, R-squared, and Pearson's correlation coefficient.

Hgb Values
Scatter plot of Change from Baseline in Hgb at Week 4 vs covariates of interest

 The following scatter plot figures will be produced separately: 
 Change from baseline in Hgb (g/dL) at Week 4 vs. Baseline body weight (kg) Change from baseline in Hgb (g/dL) at Week 4 vs. Baseline Hgb (g/dL) Change from baseline in Hgb (g/dL) at Week 4 vs. Prior ESA dose Different displays by prior ESA use will be used to differentiate them. Vertical axis will indicate the change from baseline in Hgb (g/dL) at Week 4, horizontal axis will indicate the covariates of interest, baseline body weight (kg), baseline Hgb (g/dL), or prior ESA dose (IU/week). Only individual plots will be provided unlike the scatter plot of Hgb assessments.
Scatter plot of Mean Dose during Week 40 to 52 vs. Covariates of Interest

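### No estimator is named for the between-arm difference in time within the Hgb target range, and the plan's descriptive default implies one that ignores both randomization strata

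*SAP*

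**What the plan says.** SAP Section 7.3.2 plans summaries by arm of time within, above and below the target range. For the ITT population it adds that treatment differences and 95% CIs "for the time (weeks and percentage) within the target range will also be provided", and it refers to Section 15.6.3 for details. Section 15.6.3 sets out the linear interpolation for one subject and says who is left out (subjects withdrawn from treatment before Week 40). It gives no formula or model for the difference between arms or its interval.

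Section 7.3.5 supplies the default: unless something else is specified, "endpoints / variables defined in Section 7.3.1 will be summarized using descriptive statistics, graphically presented (where appropriate) and listed". Section 7.3.5.1 specifies a model for the iron parameters only. The endpoint table in Section 7.3.1 marks a summary table and a listing for time in range, and no statistical-analysis display.

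On the design, Section 2.3 says that "subjects will be stratified by the current ESA therapy (ESA non-user or ESA user) and the Hgb level on Day 1". On covariates, Section 5.4.1 says that "Prior ESA use and baseline Hgb will be included as covariates in the principal secondary efficacy analyses". For the neighbouring endpoint, an Hgb rise above 2.0 g/dL over 4 weeks, Section 15.6.3 says: "Odds ratio and its 95% CI will be obtained using the same statistical model described in Section 7.2.5". The supplementary ANCOVA on mean Hgb over the same weeks (Section 7.1.6.2) also carries treatment, baseline Hgb and prior ESA use.

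**The concern.** Two contrasts in Section 7.3.2 are built alike: an ITT comparison, a 95% CI and a pointer to Section 15.6.3. For the rise above 2.0 g/dL the pointer leads to a covariate-adjusted logistic model. For time in range it leads to no model. A programmer who follows the text would most naturally produce a raw difference in means.

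After stratified randomization, the usual two-sample standard error counts variation between strata that the design has already balanced. If the strata predict the outcome, the interval is then wider than it needs to be, and imbalance in baseline Hgb within strata stays in the estimate. Section 5.5 says that other secondary endpoints are compared at a two-sided 5% level, so the interval will be read inferentially.

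The plan's own reasoning favours adjustment. Table 1 in Section 2.1 adds prior ESA use to the ANCOVA because it is thought to matter for Hgb. Section 5.4.1 leaves it out of the primary model because the data are longitudinal, and sees no such difficulty for an endpoint without visits. Time in range is one value per subject.

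**Working it through.** The SAP gives no SD, R², power or CI width for this endpoint, so there is no figure of its own to reproduce.

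**Inputs from the SAP.** About 286 ND subjects, 1:1 (Section 2.3). Four strata: ESA non-users with Hgb up to or above 9.5 g/dL, and ESA users with Hgb below or at least 11.0 g/dL (Section 5.4.2). The number analysed falls below 286 because of withdrawals before Week 40.

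**Assumed.** R², the within-arm variance of time in range explained by baseline Hgb and prior ESA use, from 0 to 20%. For the example in percentage points: SD 40 and 120 subjects per arm.

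**Width.**
- Unadjusted half-width = 1.96 × SD × √(2/n).
- Adjusted half-width = unadjusted × √(1 − R²).
- Example: 1.96 × 40 × √(2/120) = 10.1 points unadjusted.

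| R² | √(1 − R²) | Adjusted CI narrower by | Example half-width |
|---|---|---|---|
| 0 | 1.000 | 0% | 10.1 |
| 2% | 0.990 | 1.0% | 10.0 |
| 5% | 0.975 | 2.5% | 9.9 |
| 10% | 0.949 | 5.1% | 9.6 |
| 20% | 0.894 | 10.6% | 9.1 |

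**Coverage, by simulation.** 286 subjects were allocated 1:1 within the four strata, with a true difference of zero and 4,000 runs per R². Assumed: 60% ESA users; baseline Hgb normal with mean 11.2 and SD 0.8 in users, mean 9.8 and SD 0.6 in non-users; a normal outcome that is linear in both covariates.

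| R² | Unadjusted 95% CI covers | Width, unadjusted / ANCOVA |
|---|---|---|
| 0 | 95.4% | 1.00 |
| 5% | 95.4% | 1.03 |
| 10% | 95.6% | 1.05 |
| 20% | 97.0% | 1.12 |

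ANCOVA coverage stayed between 94.8% and 95.2%. The Monte Carlo standard error is about √(0.95 × 0.05 / 4,000) = 0.34 points, so the first three unadjusted values cannot be told apart from one another, and all lie within two standard errors of 95%.

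**Check against the closed form.** If the strata balanced all of the explained variance exactly, coverage would be 2Φ(1.96/√(1 − R²)) − 1, which is 96.1% at R² = 10% and 97.2% at 20%. The simulated values are a little lower because only dichotomised Hgb is stratified, so part of the explained variance is not balanced.

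**The case against.** A reader might infer that the SAP prescribes an unadjusted analysis. It does not say so. The default in Section 7.3.5 applies only where nothing else is specified, and Section 7.3.2 does ask for more than description. The missing statistical-analysis mark in Section 7.3.1 is not decisive either: the endpoint of a rise above 2.0 g/dL is also marked as summary only, yet it has an adjusted model. The table shells are separate documents (Section 15.11) and cannot be checked here. What stands is that no estimator is named, and that unadjusted is the natural reading of the default.

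A reader might also infer that the interval is certainly too wide. That needs the strata to predict the outcome. Dose is adjusted every 4 weeks from Week 4 towards the target, so about 36 weeks of titration precede the measurement. Values both below and above range reduce the endpoint, which weakens a linear baseline term. A small R² is plausible, and the loss may be close to nil.

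Nor is adjustment for both strata a uniform rule in this plan. The primary MMRM omits prior ESA use, with reasons given, and the change in oral iron dose (Section 7.3.2) likewise has a difference and CI without a model. Adjustment would not align this contrast fully with the principal secondary endpoint, which is an odds ratio in mITT. These points limit the consequence. They do not supply the missing method, and the planned summary by prior ESA use is a subgroup display, not an adjustment.

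**Conclusion.** The point holds as a gap in specification with a modest consequence. A 95% CI is promised with no stated estimator, and the default implies one that ignores both randomization strata, although the plan adjusts for both factors in the principal secondary logistic model, the odds ratio for a rise above 2.0 g/dL and the supplementary ANCOVA.

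The cost in precision depends on an R² that the SAP does not give: 0 to about 5% of CI width for R² of 0 to 10%, and about 11% at 20%. The SAP offers no basis for expecting the upper end. Any error is conservative. The documents do not support a reading of systematic bias or of a raised false-positive rate, because an unadjusted difference is unbiased over randomization. Stratification leaves only chance imbalance within strata, plus whatever follows from dropping subjects withdrawn before Week 40; adjustment addresses the measured part of either. The endpoint is complementary or exploratory under Section 5.5, and no confirmatory claim depends on it.

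**What to change.** State in Sections 7.3.2 and 7.3.5 that the ITT difference in time in range, in percent and in weeks, and its 95% CI come from an ANCOVA with treatment, baseline Hgb and prior ESA use, as in Section 7.1.6.2. A heteroscedasticity-robust standard error is a sensible option because the measure is bounded. Keep the descriptive summaries by arm and by prior ESA use.

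The cost is one sentence in the SAP and one model call. No new data are needed, and essentially nothing is lost if the covariates prove weak: at R² = 0 the simulated widths are equal.
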